1. STUDY SUMMARY

The TRiAD study is a multi-center, multi-country Prospective Pragmatic Cohort study assessing the effectiveness, feasibility, acceptability, and cost-effectiveness of implementing the Xpert MTB/XDR (Xpert XDR; Cepheid) assay for rapid triage-and-treatment with short, all-oral drug resistant tuberculosis (DR-TB) treatment. The proposed study aims to screen approximately 4800 GeneXpert MTB/RIF or Ultra MTB-positive participants or any currently available Nucleic Acid Amplification Tests for drug-resistance detection changes (irrespective of rifampicin resistance status) from clinical research sites in South Africa, Nigeria and Ethiopia to enrol 880 rifampicin resistant (RR) and 400 rifampicin sensitive and isoniazid, fluroquinolone and or second line injectable drug (SLID) resistant participants over a period of 12-18 months. The Xpert XDR assay, a rapid genotypic test, will be implemented as a reflex test to detect resistance to isoniazid, fluoroquinolones and second-line injectable agents to provide rapid genotypic susceptibility testing for DR-TB detection. Participants that test positive for *Mycobacterium tuberculosis* (*M.tb*) with rifampicin resistance will be enrolled in *Cohort 1* (n=880). Participants that test positive for *M.tb* that are rifampicin susceptible with isoniazid, fluroquinolone and or second line injectable drug (SLID) resistant will be enrolled in *Cohort 2* (n=400). Results from the Xpert XDR assay will be used to guide selection of appropriate, evidence-based, all-oral DR-TB treatment regimens of shortest possible duration. The tuberculosis molecular bacterial load assay (TB-MBLA) will be used as an adjunct to provide bacillary load monitoring over the course of treatment to assess real-time treatment response. Operational research will provide information about the feasibility, acceptability and cost-effectiveness to inform policies and guidelines for programmatic implementation of the triage-and-treat model.

[figure not shown]
Table 1 Overview of TRiAD Study

Study Aim	To evaluate the effectiveness, operational feasibility, acceptability, and cost-effectiveness of implementing the Xpert MTB/XDR assay for rapid triage and selection of all-oral regimens for Drug-Resistant Tuberculosis (DR-TB)
Study Design	Prospective Pragmatic Cohort Study: non-randomized interventional phase 4 (clinical access protocol) implementation science study utilizing interventions of proven clinical efficacy

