Study Duration	48 months: study enrolment will occur over 12 -18 months
Sample Size	A total of 1280 participants will be enrolled between 2 prospective study cohorts: Cohort 1 (newly diagnosed DR; rifampicin resistance [RR-TB] participants; n=880) and Cohort 2 (rifampicin sensitive and isoniazid, fluroquinolone and or second line injectable drug (SLID) resistant participants; HR-TB; n=400). Data from a historical cohort (Cohort 3; n=220) of RR-TB participants that accessed DR-TB care at each implementing site over the last 2 years (approximately 24 months) prior to study start.

Study sites	South Africa (n=2), Nigeria (n=6) and Ethiopia (n=5)
Study population	Adult participants (18 years and over) who test positive for pulmonary M.tb with HR-TB or RR-TB will be approached for study participation
Study intervention	Xpert MTB/XDR assay as a triage test to guide early initiation of an appropriate all-oral DR-TB treatment regimen

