3. DEFINITIONS OF DR-TB

- HR-TB is defined as resistance to at least isoniazid without rifampicin resistance
- RR-TB is defined as resistance to at least rifampicin without isoniazid resistance

Definitions of MDR-TB, pre-XDR and XDR-TB in background sections of this protocol refer to old WHO definitions:

- MDR-TB; resistance to at least rifampicin and isoniazid
- Pre XDR-TB; strains that fulfil the definition of MDR-TB with additional resistance to the aminoglycosides or fluoroquinolones
- XDR-TB; strains that fulfil the definition of MDR-TB with additional resistance to the aminoglycosides and fluoroquinolones.

For the purpose of defining DR-TB categories in the current study we will utilise updated 2021 WHO definitions to categorise pre-XDR-TB and XDR-TB (32)

- Pre-XDR TB; strains that fulfil the definition of RR-TB/MDR-TB with additional resistance to any fluoroquinolone
- XDR-TB; strains that fulfil the definition of RR-TB/MDR-TB with additional resistance to any fluoroquinolone and at least one additional group A drug (BDQ or LZD).

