6.2. Selection of Participants

Approximately 4800 participants will be screened across the 13 sites (in South Africa, Nigeria and Ethiopia) to enrol 1280 eligible participants. All presumptive TB patients presenting for diagnosis at the study sites will be approached for screening. Each of the sites will also contribute to the historical cohort as described below.

6.2.1. Selection of cohort 1

880 RR-TB (n=440 in SA, n=220 in Nigeria and n=220 in Ethiopia) participants will be enrolled into Cohort 1. Each participant in cohort 1 will be followed up for the duration of TB treatment and passively thereafter to a maximum of 18 months from TB treatment initiation.

6.2.2. Selection of cohort 2

400 HR participants into Cohort 2 (n=200 in SA, n=100 in Nigeria and Ethiopia). Each participant in cohort 2 will be followed up passively for the duration of TB treatment and passively thereafter to a maximum of six months.

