6.2.3. Selection of Historical Cohorts

Each CRS will build a dataset of historical RR-TB participants that were diagnosed and started on treatment within 12 - 18 months prior to starting enrolment of the study at each of the clinical research sites. Clinical and laboratory data from this retrospective cohort will be obtained from treatment registers, participant charts and laboratory databases at each of the clinical research sites. The following data variables will be extracted: date of birth, or age, sex, HIV and ART status, facility or clinic, year and month of treatment, type of DR-TB, certainty of diagnosis (confirmed by DST or presumed, i.e., contact of DR-TB source case or failing adherent first-line TB treatment), disease classification, treatment start date and any bacteriological results on treatment (date, mycobacterial culture, DST and genotypic results), where relevant. Data on all drugs from previous DR-TB treatment regimen, DR-TB Outcomes: cure, completion, default, death, loss to follow up (LTFU) will be abstracted. Historical data will be collected on specially designed case report forms (CRF) and will be subject to routine quality assurance/control QA/QC of data to ensure maximum quality. Bias by time period and by other confounders such as HIV, gender and age, will be controlled for in the analysis. No historical data will be generated for cohort 2, as no routine data on HR-TB is available.

6.3. Participant Inclusion Criteria for cohorts 1 and 2

1. Ambulant adults \geq 18 years of age
2. Newly diagnosed PTB patients receiving less than 5 days of treatment since new diagnosis:
 - a) Cohort 1: < 5 days of DR-TB treatment
 - b) Cohort 2: < 5 days of INH mono-resistant TB treatment preceding study entry for the current TB episode, or
3. Sputum positive (smear and or culture) TB patients classified as failing first line treatment
4. Any currently available Nucleic Acid Amplification Tests for drug-resistance detection changes/assay positive for M.tb infection with:
Cohort 1: at least Rifampicin resistance

- Cohort 2: Rifampicin susceptible co-occurring with INH, fluoroquinolone, ethionamide or aminoglycoside resistance (detected by Xpert XDR) occurring alone or in combination
5. Capacity to provide informed consent
 6. HIV infected and uninfected participants are allowed in the study. Participants already on ART will be allowed in the study provided the ART regimen in use has no contraindications to the proposed TB drug regimen

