6.6. Screening Procedures

Two screening strategies will be adopted:

- a) Patients with suspected pulmonary TB or confirmed *M.tb* positive (< 5 days since treatment initiation) will be screened and consented to provide an additional sputum sample for Xpert MTB/XDR testing *if required*. This will be *based on* the routine sample collected for any currently available Nucleic Acid Amplification Tests for drug-resistance detection changes
- b) We will concurrently contact all patients with newly identified RR-TB during the study enrolment period directly for participation in this study (laboratory records)

The site investigator (or designate) will assess eligibility and ensure that the participant meets study inclusion criteria. Xpert MTB/XDR (Cepheid) will be implemented as an additional DR-TB screening test. All participants must test positive for *M.tb* and participants with RR-TB will be screened for additional resistance and enrolled in Cohort 1 (estimated n=880) while those without RR will be screened for isoniazid resistance and enrolled in Cohort 2. Participants with HR-TB will be enrolled in Cohort 2 (estimated n=400). As this is an operational study, accrual

into the study will be within a specified time frame. Overview of screening and enrolment approach is outlined in figure 3.

[figure not shown]

Figure 3: Study screening and enrolment for the TRIAD Study

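### Cohort 2 is named and sized as HR-TB, but inclusion criterion 4 also admits rifampicin-susceptible participants without isoniazid resistance

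*Protocol*

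**What the plan says.** The protocol describes cohort 2 in three ways.

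**Isoniazid resistance required.** Section 3: "HR-TB is defined as resistance to at least isoniazid without rifampicin resistance". Section 6.2.2 plans "400 HR participants into Cohort 2". Section 6.6 says "those without RR will be screened for isoniazid resistance and enrolled in Cohort 2", and then that participants with HR-TB enter cohort 2. Section 9.1 starts from an assumed HR-TB frequency of about 10% per site and concludes that 400 gives about 100 HR-TB participants per site. Sections 6.2.3 and 9.2 also equate cohort 2 with HR-TB when they explain why it has no historical comparison.

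**Isoniazid resistance not required.** Section 6.3, criterion 4, for cohort 2: "Rifampicin susceptible co-occurring with INH, fluoroquinolone, ethionamide or aminoglycoside resistance (detected by Xpert XDR) occurring alone or in combination". Criterion 2b in the same list limits prior treatment only in terms of isoniazid mono-resistance: "< 5 days of INH mono-resistant TB treatment preceding study entry".

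**A third list.** In the study summary, participants who are "rifampicin susceptible with isoniazid, fluroquinolone and or second line injectable drug (SLID) resistant will be enrolled in" cohort 2. Table 1 repeats this list and attaches the label: "rifampicin sensitive and isoniazid, fluroquinolone and or second line injectable drug (SLID) resistant participants; HR-TB; n=400". Neither names ethionamide.

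Downstream, section 5 lists four categories that the assay will identify: HR-TB, rifampicin mono-resistance, MDR-TB and pre-XDR-TB. Table 2 has one row for rifampicin-susceptible disease, HR-TB.

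**The concern.** Eligibility fixes the population to which every cohort 2 result refers, and it belongs in the protocol. If criterion 4 is applied as written, a person with resistance only to a fluoroquinolone, ethionamide or an aminoglycoside enters a cohort that the protocol calls HR-TB but does not have HR-TB by section 3. Results reported for HR-TB would then describe a mixture, and the planned number with HR-TB would be an upper limit.

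Section 9.2 shows how the reading changes a result. It computes HR-TB prevalence in cohort 2. Taken literally, with cohort 2 as denominator, that is 100% by construction if isoniazid resistance is required, and a composition share if it is not. (Section 4.5 assigns the same outcome to cohort 1, which also needs reconciling.)

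The triage scheme has a matching gap. The protocol sorts participants by resistance pattern, yet neither section 5 nor Table 2 has a category for people whom criterion 4 admits without isoniazid resistance.

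**Working it through.** **Step 1. The plan's own totals.** Section 6.2.2 gives 200 + 100 + 100 = 400 for South Africa, Nigeria and Ethiopia, and 880 + 400 = 1280 matches the total enrolment. These sums are consistent. What differs is what the 400 counts.

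**Step 2. The definitions applied to four types of rifampicin-susceptible participant.** I treat aminoglycoside (6.3) and second-line injectable (summary, Table 1) as one class, although the terms are not identical.

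| Resistance found | 6.2.2, 6.6, 9.1, read with section 3 | 6.3, criterion 4 | Summary and Table 1 |
|---|---|---|---|
| Isoniazid, with or without others | in | in | in |
| Fluoroquinolone only | not described | in | in |
| Injectable / aminoglycoside only | not described | in | in |
| Ethionamide only | not described | in | not listed |

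All three versions include isoniazid resistance. They differ on whether it is necessary and on whether ethionamide resistance alone is enough. Criterion 4 expressly allows any one of the listed resistances to suffice, so an isoniazid requirement cannot be read into it. The joining words in the summary and Table 1 are looser, but the natural reading is also that isoniazid resistance is not necessary.

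**Step 3. Criterion 2b against criterion 4.** The prior-treatment limit for cohort 2 refers only to treatment for isoniazid mono-resistant TB. For a participant admitted under criterion 4 without isoniazid resistance, it is unclear what the limit refers to.

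**Step 4. Effect on the planning figure.** Let *s* be the share of cohort 2 without isoniazid resistance. Then:

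- number with HR-TB = 400 × (1 − *s*)
- number with HR-TB per planned 100 = 100 × (1 − *s*)

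The protocol gives no value for *s* and no prevalence of these other resistances among rifampicin-susceptible patients. The values below are assumptions that only show how the arithmetic moves.

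| Assumed *s* | HR-TB among 400 | HR-TB per planned 100 |
|---|---|---|
| 0 | 400 | 100 |
| 5% | 380 | 95 |
| 10% | 360 | 90 |
| 20% | 320 | 80 |
| 30% | 280 | 70 |

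Only *s* = 0 gives the figures in 6.2.2 and 9.1. That value is guaranteed if isoniazid resistance is an entry requirement and is not guaranteed under criterion 4.

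**The case against.** The best defence is that section 6.3 is the governing eligibility text. Section 6.6 has the site investigator confirm that inclusion criteria are met, and section 12.2 has the medical monitor support this on request. On that view, 6.2.2 and 6.6 are narrative, they do not say that isoniazid resistance is the only route in, and HR-TB in Table 1 is shorthand for cohort 2. This stands in part. A reader might infer that sites will in fact enrol different patients depending on the section they follow. The protocol supports a risk of that, not a certainty. But the defence leaves the main point intact: if 6.3 governs, the cohort is not HR-TB as section 3 defines it.

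A reader might also want a count of mislabelled participants. The protocol supports none, and the values in Step 4 are not estimates.

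Nor can 400 be shown to derive from the isoniazid definition. One can compute (4800 − 880) × 10% = 3920 × 10% = 392, which is close to 400. The protocol does not show that calculation, and a note to the study overview says that Xpert XDR screening is restricted to RR-TB once cohort 2 is full. So 3920 is not a reliable count of rifampicin-susceptible patients tested.

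Separate reporting is partly possible already. Entry rests on an individual Xpert XDR result, and section 9.2 stratifies several cohort 2 outcomes by type of DR-TB. An analysis-set rule could also sit in a statistical analysis plan, which is not at hand. That softens the analysis part. The entry criterion and the label remain protocol matters, and section 3 defines no type for the participants in question.

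Finally, the missing row in Table 2 does not mean that care has no stated basis. Section 5 also allows regimen choice by WHO and in-country guidelines, and section 7.1 refers cohort 2 to the national programme. The gap is in the protocol's own classification.

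**Conclusion.** The inconsistency is real and should be corrected. The protocol labels and sizes cohort 2 as HR-TB while its inclusion criterion does not require isoniazid resistance, and the summary and Table 1 differ again by omitting ethionamide. Some of the 400 may not have HR-TB; how many cannot be computed from the document.

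The stakes are moderate. Section 9.2 computes both primary endpoints in cohort 1 only, cohort 2 has no historical comparator, and section 9.1 gives no power calculation for it. Primary power and the primary comparison are unaffected. What is affected is the meaning of the cohort 2 label, the planned number with HR-TB, and the secondary outcomes reported under that name. The conclusion rests on reading criterion 4 literally and on section 3 as the definition of HR-TB. It does not depend on any assumed prevalence.

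**What to change.** 1. State one cohort 2 criterion in identical terms in the summary, Table 1, 6.2.2, 6.3 (criteria 2b and 4) and 6.6. Which one is for the sponsor to decide.
2. If isoniazid resistance is required, the HR-TB label and the figures of 400 and about 100 can stand.
3. If the wider criterion is kept:
   - drop HR-TB as the name of the whole cohort;
   - restate the 400 and the 100 per site as total cohort 2 enrolment;
   - compute any outcome labelled HR-TB only in participants with isoniazid resistance on Xpert XDR, and report the others separately. This rule may sit in the protocol or the analysis plan.
4. Reconcile section 5 and Table 2 with whoever is admitted. No regimen is proposed here.

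The cost is protocol wording. No new data are needed, because the Xpert XDR test used for entry covers isoniazid. The one drawback is that, under the wider criterion, the HR-TB analysis set may be smaller than 400.

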6.4. Participant Exclusion Criteria

Study participants will be excluded if one or more of the following conditions apply:

1. Has a known severe allergy to any of the BPaL component drugs
2. Has DST showing infection with a strain resistant to any of the component drugs
3. Has TB meningitis, other central nervous system TB, or TB osteomyelitis; or
4. Is pregnant or breastfeeding
5. Is unable to take oral medications
6. Persons with any other medical condition, precluding study participation based on investigator judgement
7. Any co-existing condition that in the opinion of the attending clinician renders the participant unsuitable for participation in the study
8. Co-enrolment in other interventional research studies

6.5. Late Exclusion Criteria

1. Resistance to BPaL component drugs on pDST conducted post study enrolment

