4.4.2. Microbiological

- To assess time to culture conversion, cure, and rates of clinical TB relapse
- To determine the prevalence of HR-TB stratified by geographic location
- To determine the prevalence of pre-XDR and XDR-TB using phenotypic DST to bedaquiline, pretomanid and linezolid
- To determine the proportion of participants with bedaquiline and linezolid resistance warranting a switch from short-course treatment
- To assess the clinical utility of the TB Molecular Bacterial Load Assay (TB-MBLA) as a predictor of treatment outcome
- To assess the diagnostic and clinical performance of the test and triage approach by geographic location using whole genome sequencing (WGS) and Minimum Inhibitory Concentration (MIC) analysis
- To determine the phylogenetic structure and full drug resistance patterns of study samples, including bedaquiline, linezolid, levofloxacin and pretomanid

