7.2. General Mycobacteriology

The following bacteriological tests will be performed at the local reference laboratory as per standard practice: smear, culture, diagnostic LPAs and pDST to BDQ and LZD in pre-XDR TB participants. At each visit, one early morning sputum sample will be tested for acid-fast bacilli (AFB) smear and culture. Study specific procedures assays will be carried out according to procedures described in the study laboratory manual. Sub-cultures will be shipped to Tuberculosis Supranational Reference Laboratory, San Raffaele Scientific Institute (OSR) for specialized tests such as MIC and WGS.

Table 5: Overview of microbiologic assessments performed after each visit

Visit	Sample Type	Microbiologic Assessments	
		Routine Testing	Study Intervention
Screening	< 2x Sputum samples	
 Direct microscopy for AFB; currently available Nucleic Acid Amplification Tests for drug-resistance detection changes, Hain Assay MTBDRplus and MTBDRs/ Culture for the presence/absence of M.tb Phenotypic DST to bedaquiline and linezolid 	
 GeneXpert XDR test¹
Enrolment	Sputum X2		
 Culture for presence/absence of M.tb Sub-culture for storage and shipment for MIC and WGS³ Sputum collection for TB-MBLA processing ²
All visits post screening	Sputum X2	
 Culture for the presence/absence of M.tb 	
 Sputum collection for TB-MBLA processing ² Any culture positive sample obtained during or after treatment will be stored at site level (optional)

Notes:

¹Xpert XDR testing: will be conducted on sputum sample collected at the screening visit following initial TB diagnosis by currently available Nucleic Acid Amplification Tests for drug-resistance detection changes. The Xpert MTB/XDR assay will be conducted in real-time to evaluate INH and second-line resistance and recommend the appropriate treatment regimen. This test will be conducted once off at the initial visit.

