²TB-MBLA testing: the test will be conducted on stored sputum samples. The test will be conducted using LifeArc TB-MBLA test kits. This assay will be conducted to assess the clinical utility of the assay, not for clinical management. It is a reverse transcription quantitative polymerase chain reaction (RT-qPCR) assay that uses 16S-rRNA as a marker to detect and quantify the load of viable *M.tb* bacteria in a participant's sputum sample. The process starts with RNA isolation from *M.tb* bacteria, followed by RT-qPCR to quantify the RNA, then conversion of the RT-qPCR output (cycle threshold [CT] values) into bacterial load values (estimated colony forming units per millilitre [eCFU/ml]) using a standard curve.

³Culture for storage, MIC and WGS: Isolates will be cultured from sputum samples collected at the screening/enrolment visit using the BD BACTEC MGIT 960 culture system at National Reference TB Laboratory. Cultured isolates will be stored at -80 degrees Celsius for further processing. 70% of clinical isolates will be sent to the study reference laboratory; OSR. OSR will perform quality assurance assessments of the Xpert MTB/XDR cartridge to be tested. The drug patterns of resistant strains detected with the XDR assay will be fully characterized by OSR. In parallel, OSR will populate and develop a catalogue of resistance of the sites, complemented by MIC testing, and seek to identify resistance markers to guide future diagnosis and treatment decisions. WGS testing will be conducted on 70% of total samples from participants with RR-TB and HR-TB enrolled from all sites in cohort 1 and 2, respectively. MIC testing for full phenotypic DST will be prioritized on a subset of 480 samples maximum, including strains with unknown mutation patterns and/or from participants failing the proposed regimen. The accuracy of Xpert MTB/XDR test results for drug resistance prediction will be assessed and quality controlled by WGS analysis. One aliquot of viable isolates from study samples will be referred from sites to OSR, arranging one shipment in year 1 and two shipments per year in the years 2, 3, 4.

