8.2. Discontinuation of treatment due to toxicity or treatment failure

The study regimens will be discontinued in some participants. In such cases, participants will be evaluated by the MMT and switched to an individualized regimen, based on the WHO guidelines for regimen design. The most common situations in which the regimen may be discontinued include:

- **Intolerable severe toxicity.** One or more drugs may need to be suspended permanently due to severe toxicity. In such cases, the clinical committee should review the medical history carefully to determine how the regimen should be modified (see discontinuation/modification criterion below).
- **Treatment failure.** If clinical and bacteriological responses to treatment are poor, a change in the treatment regimen should be considered. DST should be repeated if culture is still positive at month 4, whether or not the regimen is changed, in order to inform future management decisions.
- **Resistance to drugs in the regimen.** For participants who submit a sputum sample for culture-based second-line DST at the beginning of treatment, results may not be available until after treatment has started. If resistance to component drugs is discovered after treatment is initiated, it may be necessary to modify, extend treatment duration or discontinue the regimen.
- **Pregnancy during treatment.** For participants who become pregnant during treatment, it may be advisable to modify or discontinue novel regimens. A decision regarding continuation or discontinuation of the regimen should be made after a review by the study MMT and discussion with the participant

For participants discontinued from study treatment or whose treatment is changed and participants referred to the NTP, every effort should be made to continue passive follow up (at a reduced frequency if necessary), unless the participant has specifically withdrawn consent for further follow-up. In this event, a final status form should be completed. Details for management these participants will be outlined in a study specific SOP.

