The estimated XDR prevalence among MDR cases is 4.3% in South Africa (2018 Global TB report), 0.6% and 0.7% in Nigeria and Ethiopia (2019 Global TB report). This would mean that N=880*4.3% = 38 XDR cases. As BPaL eligibility extends to pre-XDR patients and treatment intolerant MDR patients, it is expected that a higher number will be on BPaL. A total of 40 participants (including 15% LFU) are needed to detect an improvement from 53% to 85%. This number should be possible for all sites together. Assuming approx. 10% HR-TB in each site, we aim to enrol N=400 in cohort 2 which would allow for approximately 100 HR-TB participants per site, which should be sufficient for studying associated secondary study outcomes.

9.2. Analysis including statistical methods:

Primary endpoint analysis:

- The time to appropriate treatment initiation will be calculated as median days (with interquartile range) between the first sputum collection date and the date of start of the regimen appropriate to the drug resistance pattern (defined as drug-resistance pattern appropriate treatment). This will be compared to the same time in the historical cohort and stratified by geographical location (study site). Confounding will be addressed by multivariable analysis.
- The proportion of favourable study outcomes [treatment cure or completion, based on the WHO definitions (5) will be calculated in the overall study population of cohort 1, and compared with the same proportion in the historical cohort, and stratified by geographical location (study site). In a secondary analysis, these proportions will also be calculated per type of DR-TB. Confounding will be addressed by multivariable analysis.

Both of these outcomes will only be calculated in the primary cohort (cohort 1), as no reliable historical data exist for either endpoint for HR-TB (cohort 2).

Secondary endpoint analysis:

- Prevalence of HR-TB stratified by geographical location. This will be calculated in cohort 2 and stratified by HIV status.
- The incidence of adverse events will be divided into adverse events and serious adverse events and calculated in proportions using both cohort 1 and 2. These will also be stratified by type of DR-TB, treatment regimen, and HIV status.
- Feasibility and acceptability (participant and health care provider perspective), stratified by type of DR-TB regimen (cohort 1 and 2)

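### Section 6.5 makes BPaL-drug resistance found after enrolment an exclusion, in conflict with 8.2, 9.2 and 4.4.2; applied as written, it would inflate treatment success in Cohort 1 only

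*Protocol*

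**What the plan says.** Section 6.5 consists of one criterion: "Resistance to BPaL component drugs on pDST conducted post study enrolment". It does not say whether the participant leaves the regimen, the study or the analysis. It also sets no limit by isolate, by regimen received or by time since enrolment.

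Four other sections bear on the same participants:

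- **Section 8.2** treats the finding as a management decision: "If resistance to component drugs is discovered after treatment is initiated, it may be necessary to modify, extend treatment duration or discontinue the regimen". For participants whose treatment is stopped or changed, "every effort should be made to continue passive follow up", unless they withdraw consent to it.
- **Section 9.2** states that the favourable-outcome proportion "will be calculated in the overall study population of cohort 1, and compared with the same proportion in the historical cohort".
- **Section 4.4.2** sets this secondary objective: "To determine the proportion of participants with bedaquiline and linezolid resistance warranting a switch from short-course treatment".
- **Section 6.2.3** builds the historical cohort from registers, charts and laboratory databases, and has no criterion that removes patients for resistance found later.

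Resistance to these drugs can come to light in several ways. Section 7.2 provides routine "pDST to BDQ and LZD in pre-XDR TB participants", and Table 5 places that test at the screening visit. Note 3 to Table 5 gives priority for MIC testing to a subset of at most 480 samples, "including strains with unknown mutation patterns and/or from participants failing the proposed regimen". Section 8.2 adds: "DST should be repeated if culture is still positive at month 4, whether or not the regimen is changed".

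**The concern.** An exclusion that acts after enrolment and depends on a later test result can remove people according to how treatment is going. The removal would also be one-sided, because the historical cohort has no matching filter. Part of any gain in treatment success could then come from the exclusion rather than from the triage-and-treat strategy. The adjustment for time period, HIV, gender and age in section 6.2.3 cannot restore people who are no longer in the data.

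Section 6.5 stands among the eligibility rules, which sites apply. If a site stopped following a participant under it, no later definition of the analysis set would recover the outcome. Sites that applied 6.5 and sites that applied 8.2 would also report different quantities, which matters for a comparison stratified by location.

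**Working it through.** **1. The plan's own yardstick.** Section 9.1 says that 220 per study site detects 74% against 85% favourable outcome with 80% power, allowing 15% loss to follow-up. I assume a two-sided 5% level, since 9.1 states none, and use the pooled-variance normal approximation. After 15% loss, 220 becomes 0.85 × 220 = 187.

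- 220 against 220: 81.8% power.
- 220 historical against 187 prospective: 78.2%.
- 187 against 187: 75.2%.
- 71% against 85% with 187 per group: 90.8%, in line with the stated 90%.

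The stated 80% is reproduced within two points on the first two readings. The planned difference of 11 points is therefore a fair yardstick.

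**2. The rules side by side.**

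| Section | What happens when resistance to a regimen drug is found after enrolment |
|---|---|
| 6.5 | Late exclusion, consequence not stated |
| 8.2 | Regimen modified, extended or stopped; passive follow-up continues |
| 9.2 | Favourable outcome computed in all of Cohort 1 |
| 4.4.2 | Participants with bedaquiline and linezolid resistance counted |
| 6.2.3 | No equivalent removal from the historical cohort |

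The case is not a rare corner. Section 2.1 puts phenotypic DST at about 4 to 6 weeks, while newly diagnosed participants enter with fewer than 5 days of treatment (6.3). Many results will therefore arrive after enrolment.

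**3. Shift per 1% excluded.** Let r be the share of Cohort 1 excluded, S the success rate among those retained and p the success rate the excluded would have had. Full-cohort success is (1 − r)S + rp, so the shift is S − [(1 − r)S + rp] = r(S − p). I take S = 74% and 85% from 9.1. For p I take 0% and 53%, the latter being the starting value of the BPaL comparison in 9.1, used here only as a stand-in. With r = 1%:

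- S = 74%: 0.21 points (p = 53%) or 0.74 points (p = 0%).
- S = 85%: 0.32 points (p = 53%) or 0.85 points (p = 0%).

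**4. Larger shares, all assumed.** Suppose there is no true difference and full-cohort success is 74%. The shift is then r(0.74 − p)/(1 − r). The last two columns give the two-sided rejection rate at p = 30%, for historical against Cohort 1 numbers before exclusion (748 = 0.85 × 880).

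| r | Shift, p = 0% | p = 30% | p = 50% | 187 v 187 | 187 v 748 |
|---|---|---|---|---|---|
| 1% | 0.75 | 0.44 | 0.24 | 5.1% | 5.3% |
| 3% | 2.29 | 1.36 | 0.74 | 6.0% | 7.0% |
| 5% | 3.89 | 2.32 | 1.26 | 8.0% | 10.6% |
| 10% | 8.22 | 4.89 | 2.67 | 19.0% | 30.4% |

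At 1% the effect is slight. At 5% or more it would matter. No row is an estimate, because the protocol gives no rate from which to choose r.

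**5. Per participant.** Excluding one failure raises success by S/n. With n = 220 that is 0.74/220 = 0.34 to 0.85/220 = 0.39 points. In the 40-participant BPaL comparison of 9.1 it is 0.85/40 = 2.1 points.

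**6. Time to appropriate treatment.** At worst the excluded are those with the longest times. The retained median is then percentile 50(1 − r) of the full cohort: 49.5 at r = 1%, 48.5 at 3%, 47.5 at 5%. The median barely moves.

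**The case against.** The strongest reply is that the sections can be reconciled. Section 6.5 does not say off study or out of the analysis. Section 8.2 covers participants taken off study treatment or referred to the national programme and asks for continued passive follow-up, with details in an SOP that is not shown. Section 9.2 names the overall Cohort 1 population, and nothing in section 9 removes anyone under 6.5. An SAP may settle the analysis set, and section 12.2 gives the Medical Monitoring Team the task of consistent management across sites. On that reading there is no bias. The reading is available, but the protocol does not state it, and the word it uses is exclusion.

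A reader might infer that the rule removes mainly poor responders. The documents do not support that. Table 5 puts routine bedaquiline and linezolid testing at screening, and 8.2 expects results from start-of-treatment samples to arrive late, so many late results would be baseline results not selected on response. The month-4 repeat DST serves management and is not specified as phenotypic. What stands is narrower: those excluded would tend to have a poor prognosis, and some would have been tested because they were failing.

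A reader might also size the effect from the XDR-TB prevalences in 9.1 (4.3%, 0.6% and 0.7%). Those figures were reported before the 2021 definition. The older definition in section 3 concerns aminoglycoside and fluoroquinolone resistance and says nothing about resistance to BPaL drugs.

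Finally, criterion 2 of section 6.4 bars patients with known resistance at entry, and 6.2.3 has no counterpart. That asymmetry is real, but it is a separate entry restriction that rewording 6.5 would not remove.

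**Conclusion.** The conflict is in the text and should be resolved. Bias in the primary comparison is conditional, not shown. It is zero if 8.2 and 9.2 govern. If 6.5 is applied as removal from the study or the analysis, favourable outcome in Cohort 1 is inflated by about 0.2 to 0.9 points per 1% excluded. That range assumes 74% to 85% success among those retained and 0% to 53% among those excluded. The total is unknown, because no bedaquiline, linezolid or pretomanid resistance rate is given. The effect on time to appropriate treatment is negligible.

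The protocol's wording on XDR-TB and BPaL, and the label on the 38 XDR cases in 9.1, are separate minor clarifications. They add nothing to this point.

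**What to change.** Reword 6.5 along these lines: a participant found after enrolment to have resistance to a BPaL drug has the affected regimen changed or stopped under section 8.2. The participant remains in follow-up, in the Cohort 1 denominator for both primary endpoints and in the resistance counts, with the actual date of appropriate treatment and the actual outcome.

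The cost is an amendment to one section. It needs no new visits, tests or sample size, since 8.2 already asks for the follow-up. The downside is a possibly slightly lower Cohort 1 success rate.
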